## ABBREVIATIONS AND ACRONYMS

[figure not shown]
AE	Adverse Event
ANX	Anxiety
CFR	Code of Federal Regulations
CRF	Case Report Form
DEP	Depression
EPDS	Edinburgh Postnatal Depression Scale
FDA	Food and Drug Administration
GCP	Good Clinical Practice
HIPAA	Health Insurance Portability and Accountability Act
HMD	Head mounted display
IRB	Institutional Review Board
NCT	National Clinical Trial
PI	Principal Investigator
SAE	Serious Adverse Event
STAI	State-Trait Anxiety Inventory
UPMC	University of Pittsburgh Medical Center
VR	Virtual Reality

## 1 Protocol Overview

Study Description	This project investigated whether a VR breathing intervention would reduce depression and anxiety symptoms in postpartum women with a history of depression and anxiety.
Study Population:	Six postpartum women with a history of anxiety or depression. All women were proficient in English reading and speaking.
Planned Sample Size:	10 women were anticipated to participate; 6 completed the study protocol
Participating Institutions (if a multi-center clinical trial)	University of Pittsburgh, UPMC Magee Women's Hospital

### 1.1 Study Schema

**Figure 1. Timeline of all Study Procedures.**

## 2 Background and Rationale

### 2.1 Background

Cognitive behavioral therapy is a basic element of treatment for postpartum anxiety (ANX) and depression (DEP). Exacerbations of existing DEP and ANX are rising in concert with the COVID-19 pandemic, with limited supply of mental health professionals that are trained to help these patients. Virtual Reality (VR) offers a potential solution to these care gaps, and VR has demonstrated success in treatment of pain, chronic disease, and other mental health conditions. However, VR effectiveness for treatment of postpartum ANX or DEP has not been investigated. The purpose of this pilot trial is to test patient feasibility and acceptability of virtual reality biofeedback program in pregnant and postpartum women for ANX and DEP outcomes.

### 2.2 Rationale

This study will assess the feasibility and acceptability of a headset-based virtual reality protocol to reduce anxiety and depression within women who have a history of anxiety or depression.

### **3 Hypotheses, Objectives and Endpoints**

#### **3.1 Hypotheses**

##### **3.1.1 Primary Hypothesis**

We hypothesized that the headset-based virtual reality system would be feasible as a management tool for the treatment of anxiety and depression and that women would find this method of treatment acceptable to use.

##### **3.1.2 Primary Aim:**

To determine the feasibility and acceptability of the use of a virtual reality breathing simulation for the treatment of anxiety and depression

##### **3.1.3 Secondary Aim:**

To identify changes in depression and anxiety from baseline to post treatment.

### **4 Research Design: Prospective Observational**

#### **Overview of Visits/Encounters with Participants:**

This is an open label, prospective pilot clinical trial. The individual patient's active participation is approximately two hours.

### **5 Human Subjects**

#### **5.1 Subject Population**

Six postpartum women with a history of anxiety or depression participated in a single VR biofeedback session.

#### **5.2 Inclusion Criteria**

- Recently postpartum (delivery within 3 months) women
- Diagnosed history of anxiety or depression

#### **5.3 Exclusion Criteria**

- Unable to participate in study procedures.
- English illiterate

#### **5.4 Recruitment Methods**

In conjunction with clinical teams in the outpatient clinics, [name] and the study team will identify patients eligible for the study, introduce the research to them, and obtain permission for the study team to approach them about potential participation. [name] has direct access to potential participants as a clinical at UPMC Magee Women's Hospital; as a consultant anesthesiologist [name] also has direct access to the same patients as a clinical caregiver and service administrative leader as the chief of obstetric anesthesia. [name] and the study team will work directly with clinical directors from each community practice to both identify and introduce the study to potential participants.

In addition to that, University of Pittsburgh Pitt+Me Registry will be used as a recruiting tool. Once a participant has contacted Pitt+Me with an interest in the study, a Pitt+Me recruitment staff will call them for a brief pre-screen. If they pass the pre-screen and agree to be further contacted for additional screening, a study coordinator will directly reach out to the interested individual for a phone screening.

## 6 Research Activities

### Summary of Experimental Procedures:

Utilizing head mounted display (HMD), smartphone with software rendering stereoscopic images to the user and heart rate/respiratory rate sensors connected and displayed. There is a 30-minute VR session involved breathing exercises: users saw objects in a virtual world which changed movements with their breathing. Measuring pre and post session anxiety and depression symptoms were measured by Edinburgh postnatal depression scales (EPDS) and State-trait anxiety inventory. Acceptability was assessed by questions, “Would you participate in another session?” and “would you participate in regular repeating sessions?”.

### 6.1 Screening Procedures

The screening procedures pertain to specifically women with a history of anxiety and depression. Medical record review will be completed to identify eligible participants for this study. Medical record review is a minimal risk activity that presents no additional risk beyond standard of care procedures. Any information obtained from these medical record reviews on subjects deemed ineligible will be immediately destroyed.

In conjunction with [name], for patients recruited during the postpartum period, the study team will identify patients eligible for the study, introduce the research to them, and obtain permission for the study team to approach them about potential participation. As stated above, as a consultant anesthesiologist [name] also has direct access to the same patients as a clinical caregiver and service administrative leader as the chief of obstetric anesthesia. Patients will be identified through existing recruitment channels from the community OBGYN clinics and through prospective review of the OR C-section schedule.

The clinical team will notify the patients of their eligibility for the study; potential participants who express interest in learning more about the study will be referred to the study coordinator team. The study team will approach and enroll them into this research. The patient will be approached by the study team to fully explain the study, answer any questions the patient might have, and obtain informed consent postpartum.

### 6.2 Research Procedures

#### Baseline Assessment:

Once informed consent is obtained subjects will complete baseline measurements which include a demographics form, State-Trait Anxiety Inventory (STAI), and Edinburgh Postnatal Depression Scale (EPDS). An intrapartum form will also be completed via medical chart review.

#### VR Assessment:

The VR intervention consists of three key hardware components required for use. 1) a plastic Virtual Reality Headset (also known as HMD: Head Mounted Display), which covers a user’s eyes and is secured to their head using elastic straps which can be tightened with Velcro. The HMD houses a 2) smartphone which runs the Flowly software and renders stereoscopic images which are presented to the user through the HMD. The phone connects to 3) a Bluetooth heart rate monitor which gathers heart rate data and clips simultaneously to the user’s ear lobe using a spring-loaded clip and to their clothing.

The subject will download an app to their smartphone that will transmit data to Amazon Web Services managed by Tamade, LLC. Subjects will be lent an iPhone if they do not have an iPhone or version that can support the VR sessions. In the case that subjects do have an iPhone 6s/6s+ or higher (iPhone 6/6+ not eligible), they will be asked to use it for the completion of the study.

Subjects will be given the mobile system VR Shinecon head mounted display (HMD) and Bluetooth sensors to provide patients Virtual Reality biofeedback sessions targeted for depression/anxiety. While the participant is using the VR intervention, the following outcome measure will be gathered: pain level, heart rate, and respiration will be taken via the device and smartphone app and stored in a database hosted by Amazon Web Services and managed by Tamade, LLC.

Subjects will then complete in a 1-hour VR session. In terms of the experience of the VANISH intervention, most exercises focus on breathing. Users will see objects in a 3D virtual world which change movements with their breathing and the user will be guided to use these in manners that manage body responses. Breathing resonance variation will be collected from the subjects during these exercises using the VR device. Training on how to complete these breathing exercises will be initiated as a part of the device-training.

Follow-up Assessment:

To conclude, a post-assessment STAI and EPDS will be repeated, as well as post-assessment feasibility questionnaire.

The subjects will participate in a total of 2-hours to complete all questionnaires and the VR session.

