## **11 Statistical Analysis**

### **11.1 General Approach**

Baseline demographic characteristics will be collected and analyzed using descriptive statistics.

Feasibility of the study is measured as the number of patients who report that the study was both 1.) easy to use and 2.) The session was worth my time.

Acceptability was measured as “yes” responses to both questions, “would you participate in another session in the future? 2. Based on your experience today, would you participate in regular repeating sessions (e.g., daily, or weekly)?”

Anxiety and depression are measured as continuous variables at baseline and after VR intervention. Due to the small sample size, only the number (proportion) of patients whose overall anxiety and depression scores changed/decreased from baseline to post-intervention will be reported.

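### The EPDS is repeated directly after one VR session with no comparator, minimum decrease or later assessment, so the proportion decreased should not be read as change in depression due to the session

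*Combined protocol and SAP*

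**What the plan says.** The secondary aim (section 3.1.3) is "To identify changes in depression and anxiety from baseline to post treatment". Section 6.2 fixes the order of events. At baseline, "Once informed consent is obtained subjects will complete baseline measurements", which include the STAI and the EPDS. The VR session follows, and then "a post-assessment STAI and EPDS will be repeated". Section 5.1 reports that the women "participated in a single VR biofeedback session".

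On duration, section 6.2 says "The subjects will participate in a total of 2-hours to complete all questionnaires and the VR session", and section 4 agrees that "active participation is approximately two hours". The summary in section 6 describes the symptom scales as measured before and after the session.

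The only planned summary is in section 11.1: "only the number (proportion) of patients whose overall anxiety and depression scores changed/decreased from baseline to post-intervention will be reported". No minimum size of decrease is set. Section 4 calls the trial open label, and no control group is described. No EPDS is planned after the one that closes the session. Section 11.2 hopes that the pilot's outcome estimates will help to size a fully powered trial.

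**The concern.** The depression half of the secondary aim rests on comparing two EPDS scores on either side of one short exposure. In this design a lower second score has several possible sources: ordinary variation on re-answering, memory of the answers just given, expectation in women who know what they received, and a real short-term shift. Nothing in the plan separates them, because there is no comparator, no threshold and no later measurement.

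The recall period adds a second difficulty. If the form asks about a period longer than the visit, the two scores describe nearly the same stretch of time, and the session can affect only a small part of the second one.

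The risk is one of interpretation. A count of women who decreased reads like a treatment response, and section 11.2 leaves open that it could feed the next trial's sample size.

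**Working it through.** The plan gives no power, effect size, SD or retest reliability, so there is no figure of its own to reproduce. Three checks are possible.

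**1. Overlap of the two recall windows.** Inputs: a gap of at most 2 hours (sections 4 and 6.2, assuming one sitting) and a recall period that the documents do not state, taken over a range.

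Share of the second window falling after baseline = 2 h / (24 h × days in window):
- 1 day: 2/24 = 8.3%
- 7 days: 2/168 = 1.2%
- 14 days: 2/336 = 0.6%

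Within one sitting these are upper values, since filling in the forms uses part of the two hours. They are fractions of time and do not estimate how much of a score change is noise. If the form asks about the present moment, this check falls away.

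**2. Decreases expected with no true change.** Inputs: n = 6 completers (section 1); independent women; symmetric retest variation; an assumed share t of women with the same score twice. The chance of a lower score is p = (1 − t)/2, and the number lower is binomial (6, p).

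| Tie share t | p | Expected number lower | P(at least 1 of 6) | P(at least 4 of 6) |
|---|---|---|---|---|
| 0% | 0.500 | 3.0 | 98.4% | 34.4% |
| 25% | 0.375 | 2.25 | 94.0% | 14.6% |
| 50% | 0.250 | 1.5 | 82.2% | 3.8% |
| 75% | 0.125 | 0.75 | 55.1% | 0.3% |

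The first row by hand: P(at least 4) = (15 + 6 + 1)/64 = 22/64 = 34.4%. The model covers random variation only. Expectation would push scores one way and is not included.

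**3. What six women can tell us.** The exact 95% interval for 4 of 6 runs from 22% to 96%, and for 3 of 6 from 12% to 88%.

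A simulation of whole-number scores (true score uniform from 5 to 20, normal error on each occasion) shows how much depends on the unknown retest error:
- Error SD of 2 points: 43.0% score lower with no change and 56.9% with a true fall of 1 point. In six women that is 6 × 0.430 = 2.6 against 6 × 0.569 = 3.4.
- Error SD of 0.5 points: 25.7% and 74.3%, or 6 × 0.257 = 1.5 against 6 × 0.743 = 4.5.

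These SDs are assumptions; the documents give none.

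**The case against.** Several points on the other side stand.

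- **Mostly noise.** A reader might infer that any decreases would be mostly re-answering noise. The documents do not support this, because they give no retest error. Recall of earlier answers makes tied scores more likely, and at 75% ties random variation alone yields 0.75 expected decreases in six. Many ties would not rescue the measure, though: they would mean that the score barely moves over the interval.
- **Incapable of showing change.** A reader might also infer that the EPDS cannot register any change over two hours. That depends on the recall period, which is not stated.
- **Same visit.** This is a strong inference, not a statement. Section 6.2 places baseline after consent without dating it and gives total time rather than the interval between forms. Section 13.2 allows remote consent, and section 10.2 mentions follow-up visits. The timeline figure in section 1.1 may settle it. If baseline came earlier, the closing EPDS still follows the session directly, and the difference would also include time unrelated to VR.
- **Limited weight.** Feasibility and acceptability are primary. Section 11.1 already confines symptom change to a count because the sample is small, with no test. Section 11.2 does not name the EPDS as the sizing input.
- **Dropping the outcome.** It may be tempting to remove EPDS change altogether. The outcome is prespecified and six women have completed, so removal would invite a charge of selective reporting.
- **Anxiety is not exempt.** The missing comparator, the any-decrease rule and expectation apply equally to the STAI.

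**Conclusion.** The point holds as one about interpretation. With the EPDS repeated straight after one session, apparently within about two hours, and with no comparator, minimum decrease or later assessment, the proportion decreased cannot be distinguished from retest variation, recall or expectation. It should not be reported as change in depression due to the session.

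The size depends on two unknowns. One is the recall period: 8.3% to 0.6% of the second window falls after baseline for windows of 1 to 14 days. The other is the tie share: a 34% to 0.3% chance of at least 4 of 6 decreases with no true change. How much of an observed decrease is noise cannot be established from the documents. The primary aim is unaffected. This is a cheap improvement to what the pilot may conclude.

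**What to change.** - **Sections 3.1.3 and 11.1:** still report the prespecified EPDS result, but label it an exploratory same-visit retest that does not estimate depression response. Show each woman's paired scores. State the form's recall period and the timing of both administrations; if they were not on the same day, give the actual interval in the label.
- **Section 11.2:** state that this EPDS result will not be used to size the full trial.
- **Anxiety:** attach the same no-comparator and any-decrease caveat. Name the STAI state score as the within-session anxiety measure, since section 11.1 refers only to overall anxiety. Record that this was specified after data collection.
- **Full trial:** plan the EPDS repeat at least one recall window after the session. REDCap, already used for electronic consent, could carry it remotely.
- **Session length:** section 6 gives 30 minutes, while section 6.2 says "Subjects will then complete in a 1-hour VR session". The two must be reconciled; none of the calculations above depends on it.

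The cost is a few sentences of wording and one small listing. The downside is that the pilot loses a headline count of depression change.

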## **7 Potential Risks and Benefits**

### **7.1 Reasonably Foreseeable Risks Related to Research**

*Risk associated with collecting and storing PHI.* Both common and infrequent risks include a loss of confidentiality.

*Risk associated with use of virtual reality devices.* No common risks are noted. Infrequent risks include the potential for patient to feel frustration, anxiety, or uncomfortable due to the device visualizations.

### **7.2 Potential Benefits**

There is no direct benefit.

## **8 Protection Against Risks**

### **8.1 Management of research related risks**

*Risks are associated with screening procedures and risks associated with Breach of Confidentiality in the collection and storage of PHI:*

There is a risk of "breach of confidentiality" of the screening procedures. To protect against this risk, all screening procedures will be done by study staff who have been completely trained in HIPPA/privacy procedures; all information will be kept in a locked and secure location; all data associated with the study screening will be stored against a random study ID number; any linkages between study ID number and patient identification will be separated, password

protected and stored behind UPMC firewall. To protect against the possibility of breach of confidentiality, all data collected will be identifiable only by a unique subject ID number, and no personal identifiers will be stored with data. Linkage files identifying subjects will be stored only in physical records that are kept in locked files accessible only by study staff; electronic data will be handled and protected as described above. Only consent forms will have identifiable information, and those will be kept in their chart separate from any data. Data will be labeled only with participant ID number. We will also conduct research interviews in a private room. We will collect only sensitive information limited to the minimum necessary to achieve the aims of our research. No sensitivity information will be shared via text-messages or emails.

## 9 Adverse Events and Serious Adverse Events

The proposed observational study will use the FDA definition of SAE. A serious adverse event is any untoward event that is thought by either the investigator to be unexpected and at least possibly related to the study and results in any of the following:

1. Death
2. A life-threatening adverse event
3. Inpatient hospitalization or prolongation of an existing hospitalization
4. A persistent or significant incapacity or substantial disruption of the ability to conduct normal life functions.
5. A congenital anomaly or birth defect
6. Important medical events that may not result in death, be life threatening, or require hospitalization may be considered serious when, based upon appropriate medical judgment, they may jeopardize the patient, or subject, and may require medical, or surgical intervention to prevent one of the serious outcomes listed above.

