### 9.1 Severity

The severity of adverse changes in physical signs or symptoms will be classified as follows:

- Grade 1 (Mild): asymptomatic or mild symptoms; clinical or diagnostic observation only; intervention not indicated.
- Grade 2 (Moderate): minimal, local or noninvasive intervention indicated.
- Grade 3 (Severe): medically significant but not immediately life-threatening; hospitalization or prolongation of hospitalization indicated; disabling; limiting self-care/ADL.
- Grade 4 (Life-threatening): consequences; urgent intervention indicated.
- Grade 5 (Death): event is a direct cause of death.

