### **9.4 Reporting Serious Adverse Events**

Any SAE, which is determined by the PI to be unexpected and at least possibly related to study, will be reported to the IRB as soon as possible. The PI report to the IRB will include all known details regarding the nature of the SAE.

Life-threatening or fatal unexpected adverse events associated with the study procedures must be reported to the IRB within 24 hours of discovery of the incident with subsequent follow-up submission of a detailed written report in accordance with the respective policies and procedures of the IRB. Outcomes of SAEs will be regularly reported to the IRB. A summary of the SAEs that occurred during the previous year will be included in the annual progress report as well as in the annual IRB renewal.

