#### **9.4.1 Adverse Events Reporting Timeline**

Life-threatening or fatal unexpected adverse events associated with the study must be reported to the IRB within 24 hours of discovery of the incident with subsequent follow-up submission of a detailed written report. The IRB will be notified by telephone or facsimile transmission of a human adverse event that is fatal or life-threatening no later than 7 calendar days after receiving the respective human adverse event information, followed by the subsequent submission of a written Safety Report. Serious and unexpected adverse events associated with the study protocol will be reported to the IRB with subsequent follow-up submission of a detailed written report in accordance with the respective policies and procedures of the IRB.

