## **10 Withdrawal of Subjects and Stopping Rules**

### **10.1 Adverse Events Requiring Discontinuation**

For this study, a serious adverse event is any untoward clinical event that is thought by either the investigator or the sponsor to be related to the study and results in any of the following outcomes:

1. Death
2. A life-threatening adverse event
3. Inpatient hospitalization or prolongation of an existing hospitalization
4. A persistent or significant incapacity or substantial disruption of the ability to conduct normal life functions.
5. A congenital anomaly or birth defect
6. Important medical events that may not result in death, be life threatening, or require hospitalization may be considered serious when, based upon appropriate medical judgment, they may jeopardize the patient, or subject, and may require medical, or surgical intervention to prevent one of the serious outcomes listed above.

If clinically important and unexpected adverse experiences or clinically important study-related adverse experiences occur, they will be recorded on the adverse event case report form.

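### Both SAE definitions build in relatedness and they disagree with each other, so read literally a serious outcome that nobody thinks related is left out of the annual SAE summary

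*Combined protocol and SAP*

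**What the plan says.** Section 9 opens by adopting the FDA definition of an SAE, which the protocol does not reproduce. The next sentence supplies the working definition: "A serious adverse event is any untoward event that is thought by either the investigator to be unexpected and at least possibly related". One of six listed outcomes must also have occurred.

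Section 10.1, headed as covering adverse events that require discontinuation, defines an SAE a second time. The six outcomes are the same, but here the event must be "thought by either the investigator or the sponsor to be related to the study and results in any of the following outcomes". Expectedness is not mentioned.

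Sections 9.2 and 9.3 treat relatedness and expectedness as ratings in their own right. Relatedness has five levels, and the lowest two are unlikely and not related.

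Section 9.4 sets the prompt-reporting rule, "Any SAE, which is determined by the PI to be unexpected and at least possibly related to study, will be reported" to the IRB. For periodic reporting it says: "A summary of the SAEs that occurred during the previous year will be included in the annual progress report", and in the annual IRB renewal.

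Three other provisions bear on the same events:

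- Section 12 sends all adverse events to the IRB by renewal at the latest, with no relatedness condition.
- The last sentence of Section 10.1 puts clinically important events on the adverse event case report form if they are either unexpected or study-related.
- Section 9.4.1 gives two time limits for fatal or life-threatening events.

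**The concern.** Seriousness, relatedness and expectedness are three different attributes of an event. Once relatedness is part of what makes an event serious, the SAE count depends on a causality judgement. A statement that no SAEs occurred would then not tell the reader that no death, hospitalization or other listed outcome occurred. It would say only that none occurred that was also attributed to the study and, under Section 9, also unexpected.

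The two definitions also differ in three ways:

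- **Expectedness:** required in Section 9 only.
- **Relatedness threshold:** at least possibly related in Section 9, related in Section 10.1.
- **Judge:** Section 9 says either and then names only the investigator; Section 10.1 names the investigator or the sponsor.

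Two staff members applying different sections could therefore classify the same event differently. At stake is how safety results are labelled and tabulated, not the feasibility, acceptability or score-change results.

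**Working it through.** No figure in the plan is involved, so the check is logical. Take an event that has one of the six outcomes. The five relatedness levels of Section 9.2 and the two expectedness ratings of Section 9.3 give 5 × 2 = 10 combinations. Apply each definition to each combination.

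| Relatedness | Expectedness | SAE under Section 9? | SAE under Section 10.1? |
|---|---|---|---|
| Definitely or probably | Unexpected | Yes | Yes |
| Definitely or probably | Expected | No | Yes |
| Possibly | Unexpected | Yes | Unclear |
| Possibly | Expected | No | Unclear |
| Unlikely or not related | Unexpected | No | No* |
| Unlikely or not related | Expected | No | No* |

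*Unless the sponsor thinks the event related although the investigator does not.

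The table shows three things.

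1. **Excluded by both.** The last two rows (2 levels × 2 ratings = 4 of the 10 combinations) are SAEs under neither definition when investigator and sponsor agree. The cause is the relatedness condition that the definitions share, not their differences. Since Section 9.4 summarises SAEs, such an event is not in the summary on a literal reading.
2. **In conflict.** A definitely or probably related but expected event (2 of the 10) is an SAE in Section 10.1 and not in Section 9. The two possibly related combinations are unclear in Section 10.1, because it does not say whether possibly related counts as related.
3. **Redundant filter.** Section 9.4 selects, from the SAEs, those that are unexpected and at least possibly related. Under Section 9 every SAE already meets both conditions, so the filter selects nothing. It has work to do only if an SAE is defined more broadly. This suggests that the two conditions were meant as reporting criteria.

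These are counts of combinations, not of events. The documents give no event data, so the number of events affected cannot be estimated.

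Next, what still captures an event in the last two rows:

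- **IRB.** Section 12 covers it as an adverse event, by renewal.
- **Case report form.** If it is clinically important and unexpected, Section 10.1 records it whatever its relatedness. Only an expected and unrelated event is not clearly covered by that sentence.
- **Fast notification.** The 24-hour rule in Section 9.4.1 does not reach it, being limited to study-associated events: "Life-threatening or fatal unexpected adverse events associated with the study must be reported to the IRB within 24 hours of discovery of the incident". The following sentence requires the IRB to be notified of "a human adverse event that is fatal or life-threatening no later than 7 calendar days after receiving" the information, and states no relatedness condition. On one reading that covers a fatal or life-threatening event whatever its cause; on another it continues the preceding sentence and shares its limits.

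None of these three routes requires the event to be classified or tabulated as serious.

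**The case against.** The strongest reply is that Section 9 first adopts the FDA definition, so the sentence after it is only a loose paraphrase. If the adopted definition governs and is broader, the annual summary may already include these events. This stands in part: the definition is not in the documents, so the protocol does not settle which reading applies. That is a reason to reconcile the text, but it prevents a claim that the events are certainly excluded. For the same reason a reader should not infer that the protocol departs from the FDA definition. That cannot be checked from the documents.

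A second reply is that exclusion by both definitions is not automatic on an investigator's rating of unlikely, because the sponsor's opinion can bring the event in under Section 10.1. This is right, and the claim is limited to events that neither party thinks related. It is also fair to say that Section 10.1 sits under a discontinuation heading, so its bearing on the annual summary is an inference.

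A third reply is that the IRB receives all adverse events anyway. This stands and sets the size of the point. A reader might infer that serious events would be hidden from the IRB or go unrecorded. Section 12 and the case report form rule in Section 10.1 do not support that.

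Finally, a reader might infer that a planned safety estimate is biased. The statistical section plans no SAE proportion, so there is no such estimate to bias.

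**Conclusion.** The point holds as a minor inconsistency. Relatedness is written into both SAE definitions and unexpectedness into one of them. The two definitions conflict on expectedness, threshold and judge, and the Section 9.4 filter makes sense only under a broader definition. On a literal reading, a serious outcome that neither investigator nor sponsor thinks related is missing from the annual SAE summary.

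The loss is in classification and tabulation as serious. The practical effect is small: Section 5.1 describes six women and a single session, Section 6.2 puts participation at two hours in total, and the aims concern feasibility, acceptability and score change.

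The conclusion rests on two assumptions: that the wording spelled out in Sections 9 and 10.1 is what staff apply, and that the annual summary uses the protocol's own SAE definition. If staff worked instead from a broader definition, the events would be in the summary and only the contradictory wording would remain.

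**What to change.** - **One definition.** Define an SAE once, in Section 9, by the six listed outcomes, and use it throughout. Rate relatedness (9.2) and expectedness (9.3) separately, and use them for SAEs only in the existing Section 9.4 prompt-reporting filter. That filter then does real work and needs no rewording. The annual summary should list all SAEs with their attribution.
- **Section 10.1.** Replace its own definition with a reference to Section 9, so that two definitions do not survive side by side. The investigator should reconcile, and state separately, which events lead to discontinuation. No rule is proposed here.
- **Results report.** The Protocol Overview says that six women completed the protocol, and rewording cannot change how their events were first classified. The report should therefore give the number of events with any of the six outcomes, with attribution, however first classified. This is the most useful step now.

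The cost is a few sentences in Sections 9 and 10.1, one line in the results report, and possibly a few more events listed as SAEs. The prompt-reporting criteria in Section 9.4 do not change.
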